1.1 Background and rationale

Overuse injuries are common among competitive Norwegian rhythmic gymnasts with a mean weekly prevalence of 37% [95% CI: 36% to 39%] and incidence of 4.2 new overuse injuries [95% CI: 3.6 to 4.9] per gymnast per year (Gram, M., Clarsen, B., & Bø, K., 2021). The knees, lower back and hip/groin were the most common injury locations. It has been postulated that reduced physical capacity (e.g strength, flexibility, stability) in the knees, lower back and hip/groin can increase the risk of injuries in rhythmic gymnastics.

In addition, more than 30% of the Norwegian rhythmic gymnasts experience urinary incontinence (UI), and 70% reported that UI negatively affected sports performance (Gram, M., & Bø, K., 2020). Few of the rhythmic gymnasts had any knowledge about the pelvic floor.

Hence, this assessor blinded cluster randomized controlled trial aims to find out whether the implementation of exercises targeting reduced physical capacity and pelvic floor dysfunction can prevent/reduce the prevalence of overuse injuries and UI.

The results from this RCT will be presented in two separate publications: **Publication I** on overuse injuries and **Publication II** on UI.

1.2 Trial Objectives

1.2.1 Primary Objective

Publication I: The primary objective is to assess if implementation of exercises targeting reduced capacity in the lower back, knees and hip/groin reduces the prevalence of overuse injuries in these areas compared with no targeted intervention.

Publication II: The primary objective is to assess if implementation of pelvic floor muscle training (PFMT) reduces the bother of UI compared with no targeted intervention.

1.2.2 Secondary Objectives

Publication I: The secondary objectives are:

- I. To assess if implementation of exercises targeting reduced capacity in the lower back, knees and hip/groin reduces the prevalence of substantial overuse injuries in these areas compared with no targeted intervention.
- II. The primary objective and the secondary objective number I) including overuse injuries in the calf/ankle/foot in addition to lower back, knees and hip/groin.
- III. To assess the self-experienced effect and progress of the exercise program related to overuse injuries in the knees, lower back and hip/groin in the intervention group.

STATISTICAL ANALYSIS PLAN for NCT05506579

Publication II: The secondary objectives are:

- I. To assess if implementation of PFMT reduces the prevalence of UI compared with no targeted intervention.
- II. The primary objective and the secondary objective number I) but restricted to gymnasts having UI.
- III. The primary objective and the secondary objective number I) but restricted to gymnasts having SUI.
- IV. To assess the self-experienced effect and progress of the exercise program related to UI in the intervention group.

1.2.3 Subgroup analysis

Subgroup analysis of gymnasts with more than/less than 15 hours weekly training load will be conducted on the following primary and secondary objectives:

Publication I: The secondary outcome number II)

Publication II: The primary outcome and all the secondary outcomes except number IV).

2 Trial Methods

2.1 Trial Design

This is an assessor blinded cluster randomized controlled trial with rhythmic gymnastics clubs as the unit of randomization. Two different interventions (preventive exercises for the knees, lower back and hip/groin and pelvic floor muscle training (PFMT)) for two different conditions (overuse injuries and UI) are combined in this design. After inclusion, all rhythmic gymnastics clubs will be randomly allocated 1:1 to preventive exercises for knee, lower back and hip/groin and PFMT or a control group with no intervention.

2.2 Randomisation

Eligible rhythmic gymnastics clubs are allocated in a 1:1 ratio between preventive exercises for knee, lower back and hip/groin and PFMT (intervention group) or a control group with no intervention, using a computer randomization procedure stratified by club size (less than 10 gymnasts/10 or more gymnasts). The randomization is blocked within each stratum, with block sizes 4 and 6 in random order.

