5.2 Analysis Methods

5.2.1 Publication 1

The outcomes prevalence of overuse injuries (primary outcome) and prevalence of substantial overuse injuries (secondary outcome) will be analyzed with multilevel mixed effect logistic regression models. The models will be fitted with outcome data from all time points (Nov, Dec, ..., June) except the baseline (Oct). The models will have a fixed effect for group (intervention vs control) and two random intercepts: gymnast and club, with gymnast nested within club. Based on the fitted model, we will present the odds ratio (OR) for injury (with 95% confidence interval [CI]) for intervention vs control and the P-value for the null hypothesis of an OR = 1.

The observed prevalence of injuries (with 95% CI) for each time point (Oct, Nov, ..., June) for the primary outcome and the secondary outcome I) and II) will be presented in a figure.

Self-experienced effect and progress is measures on a -5 to 5 scale and only measured after end of the intervention (June) and only for the gymnasts in the intervention group. We will present the observed number and percentage of responses in each category (-5, -4, ..., 4, 5) and also the mean and standard deviation of the responses.

5.2.2 Publication 2

Bother of UI (primary outcome) at the end of the intervention (June) will be analyzed with linear regression, with the June measurement as the dependent variable and group (intervention vs control) and the baseline (Oct) measurement as independent variables (ANCOVA). The standard errors in the model will be adjusted for the clustering of gymnasts within clubs. We will present the mean and standard deviation of the baseline and end-of-intervention measurements for each group and the estimated between-group difference in changes from baseline to end-of-intervention with a 95% CI. We will also give the P-value for the null hypothesis of a zero between-group difference.

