The prevalence of UI (secondary outcome) at the end of the intervention (June) will be analyzed with a mixed effect logistic regression model with the June measurement as dependent variable and group (intervention vs control) and the baseline (Oct) measurement as independent variables. The model will contain a random intercept for club to account for the clustering of gymnasts within clubs. We will present the observed prevalence of UI for each group for each of the two time points, the OR for UI (with 95% CI) for intervention vs control and the P-value for the null hypothesis of an OR = 1.

Self-experienced effect and progress will be analyzed as described in section 5.2.1.

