5.2.3 Sensitivity analyses

A sensitivity analysis of the prevalence of injuries (primary outcome in publication 1) will be performed with a mixed effect logistic regression model where only the June measurement is used as an outcome. The model will have a fixed effect for group (intervention vs control) and a random intercept for club to account for the clustering of gymnasts within clubs.

STATISTICAL ANALYSIS PLAN for NCT05506579

A sensitivity analysis of the bother of UI (primary outcome in publication 2) will be performed with a quantile (median) regression model with the June measurement as dependent variable and group (intervention vs control) and the baseline (Oct) measurement as independent variables.

6 Statistical Software

All statistical analyses will be done in Stata version 17 (StataCorp LLC, College Station, TX, USA).

7 References

Clarsen, B., et al., *The Oslo Sports Trauma Research Center questionnaire on health problems: a new approach to prospective monitoring of illness and injury in elite athletes*. British journal of sports medicine, 2014. 48(9): p. 754-760.

Clarsen, B., et al., *Improved reporting of overuse injuries and health problems in sport: an update of the Oslo Sport Trauma Research Center questionnaires*. British Journal of Sports Medicine, 2020. 54(7): p. 390-396.

Ferreira, S., et al., Reeducation of pelvic floor muscles in volleyball athletes. Revista da Associação Médica Brasileira, 2014. 60(5): p. 428-433

Olsen, O.-E., et al., Exercises to prevent lower limb injuries in youth sports: cluster randomised controlled trial. BMJ, 2005. 330(7489): p. 449.

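### Clubs are randomised in blocks within club-size strata, but no group-comparison model includes the stratum: a cheap improvement of low severity, to be made together with a small-sample correction

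*SAP*

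**What the plan says.** Section 2.2 makes the club the unit of allocation ("Eligible rhythmic gymnastics clubs are allocated in a 1:1 ratio") and randomises "using a computer randomization procedure stratified by club size (less than 10 gymnasts/10 or more gymnasts"). It adds: "The randomization is blocked within each stratum, with block sizes 4 and 6 in random order".

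The models that compare the groups are written out as follows.

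- Publication I, primary and other injury prevalence outcomes (5.2.1): "The models will have a fixed effect for group (intervention vs control) and two random intercepts: gymnast and club". Group is the only fixed effect.
- Publication II, primary (5.2.2): the regressors are "group (intervention vs control) and the baseline (Oct) measurement as independent variables (ANCOVA"), and "The standard errors in the model will be adjusted for the clustering of gymnasts within clubs".
- Publication II, prevalence of UI (5.2.2): group and baseline status, and "The model will contain a random intercept for club to account for the clustering of gymnasts within clubs".
- Publication I sensitivity analysis, June only (5.2.3): "The model will have a fixed effect for group (intervention vs control) and a random intercept for club".
- Publication II sensitivity analysis (5.2.3): median regression on group and baseline score, with no clustering adjustment stated.

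Club size appears in none of them, and the SAP gives no reason for leaving it out. Because the fixed effects are listed model by model, this is not a detail left to another document.

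**The concern.** Blocking within strata balances club size between the arms. If small and large clubs differ in injury prevalence or UI score, the between-stratum part of the club variance hardly contributes to the real error of the treatment comparison. A model without the stratum still counts that part as club-level error. A club random intercept or a cluster-adjusted standard error handles correlation within clubs, but it does not take the between-stratum part out.

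A second error has the opposite sign. With about 24 clubs, the planned cluster-robust and random-intercept standard errors tend to be too small. How well the reported intervals and p-values are calibrated then depends on how strongly club size predicts the outcome, on which the SAP is silent.

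**Working it through.** **Inputs from the SAP (2.3).** Prevalence 40% vs 20%, power 80%, two-sided 5%, m = 9, ICC = 0.05, DE = 1.4, 158 gymnasts before and 220 after inflation; for Publication II, 4.7 vs 2.5 with SD 2.1, 30 gymnasts before and 42 after. **Assumed:** the share s of between-club variance that the stratum explains, shown at 0, 10, 25 and 50% with total ICC held at 0.05.

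**1. The plan's own figures.**
- Publication I: (1.96 + 0.8416)² × (0.4×0.6 + 0.2×0.8) / 0.2² = 78.5, so 79 per arm and 158 in total. 158 × 1.4 = 221.2, against 220 stated.
- Publication II: 15 per arm gives 30, and 30 × 1.4 = 42.
- Number of clubs: 220 / 9 = 24.4.

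None of these figures is disputed.

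**2. Closed form, one time point.** With total variance 1, of which 0.05 lies between clubs, the design effect with the stratum in the model is DE(s) = 0.95 + 9 × 0.05 × (1 − s). At s = 0 this is the plan's 1.40. The width ratio without/with the stratum is √(1.40/DE(s)). Power at the matching standard error is Φ(0.2/√(0.40 × DE(s)/110) − 1.96). For scale, the share is converted to a prevalence gap between two equal strata, 2√(s × 0.05 × 0.21), taking 30% as the mean prevalence.

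| s | Gap between strata | DE(s) | Width ratio | Power |
|---|---|---|---|---|
| 0 | 0 | 1.400 | 1.000 | 80.0% |
| 10% | 6.5 points | 1.355 | 1.016 | 81.3% |
| 25% | 10.2 points | 1.288 | 1.043 | 83.2% |
| 50% | 14.5 points | 1.175 | 1.092 | 86.4% |

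**3. Publication II ANCOVA, simulated with unequal clubs.** 14 clubs of 6 and 10 clubs of 13 or 14 (84 + 136 = 220 gymnasts), blocks of 4 and 6 with incomplete blocks allowed, total ICC 0.05, baseline correlation 0.5 (assumed). The planned analysis is taken as the usual cluster-robust standard error with t on clubs minus 1 df. The correction is CR2 with Satterthwaite df.

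| | s = 0 | 10% | 25% | 50% |
|---|---|---|---|---|
| Type I error, planned | 6.24% | 5.69% | 5.13% | 3.85% |
| Type I error, stratum added, uncorrected SE | 6.81% | 6.71% | 6.90% | 6.47% |
| Type I error, stratum and correction | 5.09% | 5.14% | 5.26% | 4.99% |
| Width: stratum and correction / planned | 1.053 | 1.031 | 0.997 | 0.939 |
| Width, both corrected: without / with stratum | 0.993 | 1.014 | 1.048 | 1.112 |

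A separate run with unequal clubs and real blocks gave about 6.6, 5.6, 5.3 and 4.4% for the planned analysis, and about 6.6 to 7.0% with the stratum and the uncorrected SE.

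**4. Baseline already carrying the club-size effect.** This was run only with 24 equal clubs of 9, 12 per stratum. If gymnasts per club is meant, that layout cannot straddle a cut at 10, so only the contrast should be read from it. With correction in both models, leaving the stratum out widens intervals by 5.5% (s = 25%) and 12.1% (s = 50%). If club size shifts the baseline score equally, these fall to 1.2% and 2.9%, and the planned type I error is 4.7% and 4.8%.

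**5. Publication I eight-month model.** Three-level logistic model, latent club ICC 0.05, no missing data, 10,000 null runs (Monte Carlo SE near 5%: √(0.05 × 0.95/10000) = 0.2 points). Type I error at s = 0, 10, 25 and 50%:

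- Unequal clubs, gymnast SD 2 on the logit scale (assumed): planned 7.60, 6.51, 5.65, 4.29%; stratum with t on clubs minus 3 df 6.60, 5.94, 5.89, 4.78%.
- Gymnast SD 1: planned 6.94, 6.33, 5.50, 3.48%; stratum with t 6.04, 6.20, 6.39, 6.04%.
- Power at 40% vs 20%, equal clubs of 9 and SD 2: 97 to 99% with or without the stratum.

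**The case against.** The strongest reply is that the harm rests on an input the SAP does not supply. Nothing in it says that club size predicts injury or UI, and balancing gymnast numbers between arms would be reason enough to stratify. A share of 50% means a gap of about 14.5 percentage points between small and large clubs, and nothing in the SAP makes that likely. This stands, and it is why the result is shown as a range.

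It also stands that much of the remedy treats the small number of clubs and not the missing stratum. Adding the stratum alone moves the ANCOVA error rate further from 5% at shares of 0 to 25%. With stratum and correction together, intervals are wider than planned at shares of 0 and 10%, about equal at 25%, and narrower only at 50%. The two changes therefore belong together.

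Finally, Publication II already adjusts for baseline, which may absorb most of the club-size effect, and the Publication I model has ample power under complete data. Both points limit the gain. They do not supply a reason for leaving a randomisation factor out of every model.

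**Conclusion.** The omission is real and cheap to repair, and its severity is low. Under the assumptions above, leaving the stratum out widens intervals by 0 to 9% in closed form for shares of 0 to 50%. The planned ANCOVA's type I error runs from about 6% to about 4%, because the omitted stratum and the small number of clubs pull in opposite directions.

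A reader might infer more, and the SAP does not support it:

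- **That the treatment effect is biased or the sample size wrong.** Allocation is random within strata, and section 2.3 uses the full design effect of 1.4 with no credit for stratification.
- **That the planned analysis is generally conservative.** With unequal clubs and a share of 0 or 10%, the planned ANCOVA is mildly anti-conservative (6.2% and 5.7%). It is clearly conservative only near a share of 50%.
- **That the trial loses material power.** The rise from 80% to 86% in the closed form is for one time point. The eight-month primary model has 97 to 99% either way. In the logistic models the stratum also makes the odds ratio conditional on club size, so the gain should not be read simply as a narrower interval for the log odds ratio.
- **That the fix frees the error rate from the unknown share.** This is nearly so for the ANCOVA (5.0 to 5.3%), but not for Publication I with unequal clubs (6.6% to 4.8%).

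No claim is made about the standard errors of the median regression.

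**What to change.** In sections 5.2.1 to 5.2.3, add the club-size stratum used at randomisation as a fixed effect in both primary models, the UI prevalence model and the sensitivity models. In the same change, specify a small-sample club-level correction:

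- Publication II ANCOVA: CR2 cluster-robust variance with Satterthwaite degrees of freedom. The rest of the ANCOVA can stay as it is.
- Club random-intercept logistic models: refer the group coefficient to t on clubs minus 3 degrees of freedom. In the eight-month model this reduces the excess type I error but does not remove it.

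The stratum should not be added with the uncorrected standard errors. If the sponsor prefers to leave it out, the SAP should say why.

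**Cost.** One phrase per model, one sentence on the correction and one club-level degree of freedom; the factor is known for every randomised club. If club size is not prognostic, ANCOVA intervals become 2.5% (equal clubs) to 5.3% (unequal clubs) wider than planned. Nearly all of that comes from the correction, since the stratum itself adds 0.2 to 0.7%. At an assumed effect of 0.4 SD, adding the stratum to the corrected ANCOVA lowers power from 74.3% to 74.0% (equal clubs) or from 71.2% to 70.4% (unequal clubs). The analyst should confirm that both corrections can be obtained in the software named in section 6.

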2.3 Sample size

The power calculation for Publication I (overuse injuries) is based on average prevalence in our previous study (Gram, M., Clarsen, B., & Bø, K., 2021) and previous studies with a

STATISTICAL ANALYSIS PLAN for NCT05506579

similar design (Olsen, et.al, 2005). With 80% power, 5% significance level and a decrease in the primary outcome measure from 40% to 20% in the intervention group and no change in the control group at least 158 gymnasts are required. In addition, to account for randomization at the cluster level, the total number were multiplied with an inflation factor (DE) of 1.4 (based on the following assumptions; average number of gymnasts per club (cluster) $m = 9$, $ICC = 0.05$, $DE = 1+(m - 1)*ICC = 1+(9 - 1)*0.05 = 1.4$), resulting in a required total sample size of 220 gymnasts (110 in each group).

The power calculation for Publication II (UI) is based on average prevalence in our previous study (Gram, M., & Bø, K., 2020) and studies with a similar design (Ferreira, et.al, 2014). With 80% power, 5% significance level and a decrease in the total sum score of ICIQ from 4.7 to 2.5 (SD 2.1) in the intervention group and no change in the control group at least 30 gymnasts are required. Multiplied with the same DE, the total required sample size will be 42 gymnasts (with 21 in each group).

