2.5 Timing of Outcome Assessments

Publication I:

- Primary outcome: To assess the prevalence of overuse injuries in the lower back, knees and hip/groin, the Oslo Sports Trauma Research Center Questionnaire on Health Problems (OSTRC-H2) was used. The gymnasts in both groups answered the OSTRC-H2 at baseline (October 2022) and one time each month (last Sunday during the month) throughout the intervention period (November 2022 - June 2023).
- Secondary outcome:
 - I. To assess the prevalence of substantial overuse injuries in the lower back, knees and hip/groin, the same assessment method and time frame as listed above for the primary outcome was used.
 - II. To assess the primary outcome and the secondary outcome number I) including overuse injuries in the calf/ankle/foot in addition to lower back, knees and hip/groin, the same assessment method and time frame as listed above for the primary outcome was used.
 - III. To assess self-experienced effect and progress of the exercise program related to overuse injuries in the knees, lower back and hip/groin, a global rating of change (GRC) 11-point numerical scale was used. The gymnasts in the intervention group answered the GRC one time when the intervention period had ended (June 2023).

Publication II:

- Primary outcome: To assess the bother of UI, The International Consultation on Incontinence Questionnaire - Urinary Incontinence Short Form (ICIQ-UI-SF) was used. The gymnasts in both groups answered the ICIQ-UI-SF one time at baseline (October 2022) and one time when the intervention period had ended (June 2023).
- Secondary outcome:
 - I. To assess the prevalence of UI, the same assessment method and time frame as listed above for the primary outcome was used.
 - II. To assess the primary outcome and the secondary outcome number I) restricted to gymnasts having UI, the same assessment method and time frame as listed above for the primary outcome was used.
 - III. To assess the primary outcome and the secondary outcome number I) restricted to gymnasts having SUI, the same assessment method and time frame as listed above for the primary outcome was used.
 - IV. To assess self-experienced effect and progress of the exercise program related to UI, a global rating of change (GRC) 11-point numerical scale was used. The gymnasts in the intervention group answered the GRC one time when the intervention period had ended (June 2023).

STATISTICAL ANALYSIS PLAN for NCT05506579

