5.1.1 Primary Outcome Definition

Publication I: The primary outcome is the prevalence of overuse injuries in the lower back, knees and hip/groin during the intervention period. In the OSTRC-H2 a health problem is defined as: “any condition that you consider to be a reduction in your normal state of full health, irrespective of its consequences on your sports participation or performance, or whether you have sought medical attention. This may include, but is not limited to, injury, illness, pain or mental health conditions.” Furthermore, an overuse injury is defined as: “an injury caused by multiple accumulative bouts of energy transfer without a single, clearly identifiable event responsible for the injury.” (Clarsen, et.al, 2020; Clarsen, et.al 2014). The primary outcome is dichotomous.

Publication II: The primary outcome is the bother of UI before and after the intervention period. Degree of bother is defined with the ICIQ-UI-SF sum score (0-21 points). The primary outcome is continuous.

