5.1.2 Secondary Outcomes Definitions

Publication I: The secondary outcomes are:

- I. The prevalence of substantial overuse injuries in the lower back, knees and hip/groin during the intervention period. A substantial overuse injury is defined as “an overuse injury leading to moderate or severe reductions in sports performance or participation, or time loss” in the OSTRC-H2 (Clarsen, et.al, 2020; Clarsen, et.al 2014). The secondary outcome is dichotomous.
- II. The primary outcome and the secondary outcome number I) including overuse injuries in the calf/ankle/foot in addition to lower back, knees and hip/groin. The same definitions as listed above apply. The secondary outcome is dichotomous.
- III. The self-experienced effect and progress of the exercise program related to overuse injuries in the knees, lower back and hip/groin. The secondary outcome is continuous (score of -5 to 5).

Publication II: The secondary outcomes are:

- I. The prevalence of UI before and after the intervention period. The prevalence is defined by question 6 in the ICIQ-UI-SF. The secondary outcome is dichotomous.
- II. The primary outcome and the secondary outcome number I) restricted to gymnasts having UI. The secondary outcome is continuous.
- III. The primary outcome and the secondary outcome number I) restricted to gymnasts having SUI. The secondary outcome is continuous.

STATISTICAL ANALYSIS PLAN for NCT05506579

IV. The self-experienced effect and progress of the exercise program related to UI.
The secondary outcome is continuous (score of -5 to 5).

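### Does the 40% planning prevalence for a three-site outcome undermine the 80% power stated for 220 gymnasts in Publication I?

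*SAP*

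**What the plan says.** Section 2.3 says that the Publication I calculation "is based on average prevalence in our previous study" and on earlier studies with a comparable design. The design alternative is "a decrease in the primary outcome measure from 40% to 20% in the intervention group", with no change among controls, at 80% power and 5% significance. This gives 158 gymnasts. A design effect of 1.4 (nine gymnasts per club, ICC 0.05) raises the total to 220, or 110 per group.

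Section 1.1 reports the cohort's "mean weekly prevalence of 37% [95% CI: 36% to 39"%, with no restriction by body site. On sites it says only this: "The knees, lower back and hip/groin were the most common injury locations".

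Section 5.1.1 defines the endpoint: "The primary outcome is the prevalence of overuse injuries in the lower back, knees and hip/groin during the intervention period". The lower leg enters only in secondary outcome II of section 5.1.2, "including overuse injuries in the calf/ankle/foot in addition to lower back, knees and hip/groin".

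On measurement, section 2.5 has gymnasts answering "one time each month (last Sunday during the month) throughout the intervention period", and section 5.2.1 states: "The models will be fitted with outcome data from all time points (Nov, Dec, ..., June) except the baseline (Oct").

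**The concern.** The planning value does not match the figure quoted from its named source. The 40% lies above the cohort estimate of 37% and above its upper confidence limit of 39%. That estimate covers every site, and on the same measure a three-site prevalence cannot exceed an all-site one. The SAP gives neither a three-site prevalence nor a reason for 40%.

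If the true control prevalence were lower and the intervention halved it, the absolute difference would shrink and power would fall. The 80% at 220 is the only power statement for this endpoint, so a reader of a non-significant result could be misled about what the trial was able to detect.

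**Working it through.** **Inputs from the SAP.** Two-sided alpha 0.05 (section 2.4.2); power 80%, rates 40% and 20%, m = 9, ICC = 0.05, DE = 1.4, N = 220 (section 2.3); cohort prevalence 37% (section 1.1); eight monthly outcomes (section 5.2.1).

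**Inputs assumed.** The three-site prevalence and the within-gymnast correlation ρ between months. The SAP gives neither, so ranges are shown.

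**Step 1: reproduce the plan.** Two proportions, unpooled variance:

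n per arm = (1.960 + 0.842)² × [p₁(1 − p₁) + p₂(1 − p₂)] / (p₁ − p₂)²

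At 40% and 20%: 7.849 × (0.24 + 0.16) / 0.04 = 78.49, rounded up to 79, so 158 in total. With clustering: 2 × 78.49 × 1.4 = 219.8, so 220. Both figures reproduce.

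**Step 2: the same formula at other control prevalences.**

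Power = Φ( |p₁ − p₂| / √{[p₁(1 − p₁) + p₂(1 − p₂)] × 1.4 / 110} − 1.96 )

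| Control → intervention | Effect held fixed | Power at 220 | N for 80% |
|---|---|---|---|
| 40% → 20% | as planned | 80% | 220 |
| 37% → 18.5% | halving | 75% | 247 |
| 37% → 20% | 20% endpoint | 67% | 299 |
| 37% → 17% | 20-point drop | 83% | 206 |
| 30% → 15% (assumed) | halving | 63% | 330 |
| 25% → 12.5% (assumed) | halving | 53% | 418 |
| 30% → 10% (assumed) | 20-point drop | 90% | 165 |

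A lower control prevalence reduces power if the relative effect or the endpoint is held, and raises it if the absolute drop is held.

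**Step 3: allow for the planned model.** Step 2 treats each gymnast as one yes/no result, but the primary model uses eight months. On the risk-difference scale, with exchangeable correlation ρ within a gymnast, 0.05 between gymnasts in the same club, and complete data, the factor 1.4 becomes

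9 × 0.05 + (ρ − 0.05) + (1 − ρ)/8

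At ρ = 0.4, 0.5 and 0.6 this is 0.875, 0.9625 and 1.05. At ρ = 1 it returns to 1.4, which is the SAP's own calculation.

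| Control → intervention | ρ = 0.4 | ρ = 0.5 | ρ = 0.6 | ρ at which power is 80% |
|---|---|---|---|---|
| 37% → 18.5% | 92% | 89% | 86% | 0.83 |
| 37% → 20% | 86% | 83% | 79% | 0.58 |
| 30% → 15% (assumed) | 83% | 79% | 75% | 0.47 |
| 25% → 12.5% (assumed) | 73% | 69% | 65% | 0.24 |

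Under a halving, 220 gymnasts keep 80% power down to a three-site prevalence of 28.5%, 30.7% or 32.7% at ρ = 0.4, 0.5 or 0.6.

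**Step 4: are 37% and 40% the same measure?** The cohort figure is a mean weekly prevalence, and the title in the reference list (section 7) places that cohort in preseason. The trial takes one response per month from November to June. The rule that three sites cannot exceed all sites holds only within one measure, so 37% does not cap the trial's control prevalence.

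**The case for a change.** The strongest case for a change is that the gap is internal to the SAP. It names a source, quotes a figure from it, and then uses a higher value for a narrower outcome. Rounding could explain three points but not the site restriction. The second cited basis does not help, because no prevalence from it is quoted. The eight-month figures are also favourable: they assume complete data, while the full analysis set in section 3.3 admits a gymnast with as few as two responses, one of which may be the October baseline that the model leaves out. If the three-site prevalence were 25%, a halving would be underpowered at each of the correlations shown.

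Most of this stands as description. The source of 40% is not documented, and power below 80% is possible. It does not establish that the input is wrong. Section 2.3 rests on two bases, and neither the cohort report nor the comparable trial is at hand. The three-site prevalence may be close to the all-site one, since those sites were the commonest, or well below it.

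A complaint that section 2.3 leaves the effect scale open carries little weight. A fall from 40% to 20% is at once a halving, a 20-point drop and a 20% endpoint. These separate only when someone else changes the control rate.

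**Conclusion.** No change to the plan is needed. Section 2.3 states every input to its calculation, and 158 and 220 are correct for 40% against 20%. The 80% is conditional on those rates, as any design power is.

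The documented discrepancy is three percentage points, between a monthly planning value and a weekly preseason estimate. On the SAP's formula that moves power to between 67% and 83%, depending on the effect held. On the planned eight-month model a halving from 37% gives 86% to 92%. A shortfall under a halving needs a three-site prevalence below about 28% to 33%, or a correlation above 0.83 at 37%. These figures rest on assumed correlations of 0.4 to 0.6, complete months, a constant ICC and the risk-difference scale, so they do not prove adequate power either. The net direction is unknown.

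Nothing would be gained in the results. Section 2.5 describes data collection to June 2023 in the past tense, so the sample size can no longer respond. The outcome, model, estimate, confidence interval and decision rule would all stay the same, and the confidence interval will show the precision achieved better than a restated design power. A sentence in the publication saying where 40% comes from for the three-site outcome would be a courtesy to readers, not a correction.
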